### **Preexisting Condition**

A preexisting condition is one that is present at the start of the study. A preexisting condition should be recorded as an adverse event if the frequency, intensity, or the character of the condition worsens during the study period.

### **General Physical Examination Findings**

At screening, any clinically significant abnormality should be recorded as a preexisting condition. At the end of the study, any new clinically significant findings/abnormalities that meet the definition of an adverse event must also be recorded and documented as an adverse event.

### **Post-study Adverse Event**

All unresolved adverse events should be followed by the investigator until the events are resolved, the subject is lost to follow-up, or the adverse event is otherwise explained. At the last scheduled visit, the investigator should instruct each subject to report any

CONFIDENTIAL

This material is the property of the NYU School of Medicine and Langone Medical Center. Do not disclose or use except as authorized in writing by the study sponsor

subsequent event(s) that the subject, or the subject's personal physician, believes might reasonably be related to participation in this study. The investigator should notify the study sponsor of any death or adverse event occurring at any time after a subject has discontinued or terminated study participation that may reasonably be related to this study. The sponsor should also be notified if the investigator should become aware of the development of cancer or of a congenital anomaly in a subsequently conceived offspring of a subject that has participated in this study.

### **Abnormal Laboratory Values**

A clinical laboratory abnormality should be documented as an adverse event if any one of the following conditions is met:

- The laboratory abnormality is not otherwise refuted by a repeat test to confirm the abnormality
- The abnormality suggests a disease and/or organ toxicity
- The abnormality is of a degree that requires active management; e.g. change of dose, discontinuation of the drug, more frequent follow-up assessments, further diagnostic investigation, etc.

### **Hospitalization, Prolonged Hospitalization or Surgery**

Any adverse event that results in hospitalization or prolonged hospitalization should be documented and reported as a serious adverse event unless specifically instructed otherwise in this protocol. Any condition responsible for surgery should be documented as an adverse event if the condition meets the criteria for an adverse event.

Neither the condition, hospitalization, prolonged hospitalization, nor surgery are reported as an adverse event in the following circumstances:

- Hospitalization or prolonged hospitalization for diagnostic or elective surgical procedures for a preexisting condition. Surgery should **not** be reported as an outcome of an adverse event if the purpose of the surgery was elective or diagnostic and the outcome was uneventful.

CONFIDENTIAL

This material is the property of the NYU School of Medicine and Langone Medical Center. Do not disclose or use except as authorized in writing by the study sponsor

- Hospitalization or prolonged hospitalization required to allow efficacy measurement for the study.
- Hospitalization or prolonged hospitalization for therapy of the target disease of the study, unless it is a worsening or increase in frequency of hospital admissions as judged by the clinical investigator.

## **8.2 Recording of Adverse Events**

At each contact with the subject, the investigator must seek information on adverse events by specific questioning and, as appropriate, by examination. Information on all adverse events should be recorded immediately in the source document, and also in the appropriate adverse event module of the case report form (CRF). All clearly related signs, symptoms, and abnormal diagnostic procedures results should be recorded in the source document (though should be grouped under one diagnosis).

All adverse events occurring during the study period must be recorded. The clinical course of each event should be followed until resolution, stabilization, or until it has been determined that the study treatment or participation is not the cause. Serious adverse events that are still ongoing at the end of the study period must be followed up to determine the final outcome. Any serious adverse event that occurs after the study period and is considered to be possibly related to the study treatment or study participation should be recorded and reported immediately.

## **8.3 Reporting of Serious Adverse Events and Unanticipated Problems**

A serious adverse event (SAE) includes any event that results in any of the following outcomes:

- Death
- Initial or prolonged inpatient hospitalization
- A life-threatening experience (that is, immediate risk of dying)
- Persistent or significant disability/incapacity
- Congenital anomaly/birth defect
- Other medically important events

CONFIDENTIAL

Unexpected and related SAE will be reported to the IRB and within 5 days after study personnel become aware of the event. Serious adverse events (SAE) occurring after a participant is discontinued from the study will only be reported if the Principal Investigator believes that the event may have been caused by the study medication or a protocol procedure.

### **For Narrative Reports of Safety Events**

If the report is supplied as a narrative, the minimum necessary information to be provided at the time of the initial report includes:

- Study identifier
- Study Center
- Subject number
- A description of the event
- Date of onset
- Current status
- Whether study treatment was discontinued
- The reason why the event is classified as serious
- Investigator assessment of the association between the event and study treatment

#### **8.3.1 Investigator reporting: notifying the study sponsor**

The following describes events that must be reported to the study sponsor in an expedited fashion.

#### **Initial Report: within 24 hours:**

The following events must be reported to Shire by telephone within 24 hours of awareness of the event:

- Unanticipated problems related to study participation,
- Serious adverse events, regardless of whether they are unexpected.

CONFIDENTIAL

This material is the property of the NYU School of Medicine and Langone Medical Center. Do not disclose or use except as authorized in writing by the study sponsor

Additionally, an FDA Form 3500A (MEDWATCH Form; see Attachment [5]) must be completed by the investigator and faxed to the studyShire within 24 hours. The investigator shall maintain a copy of the MEDWATCH Form on file at the study site.

[name]- [contact]

Shire Pharmaceuticals

[name]

16

[name]

**Follow-up report: within 48 hours:**

As a follow-up to the initial report, within the following 48 hours of awareness of the event, the investigator shall provide further information, as applicable, on the unanticipated event or the unanticipated problem in the form of a written narrative. This should include a copy of the completed Unanticipated Problem form, and any other diagnostic information that will assist the understanding of the event. Significant new information on ongoing unanticipated adverse events shall be provided promptly to the study sponsor.

**Other Reportable events:**

- **Deviations from the study protocol**

Deviations from the protocol must receive both Sponsor and the investigator's IRB approval before they are initiated. Any protocol deviations initiated without Sponsor and the investigator's IRB approval that may affect the scientific soundness of the study, or affect the rights, safety, or welfare of study subjects, must be reported to the Sponsor and to the investigator's IRB as soon as a possible, but **no later than 5 working days** of the protocol deviation.

- **Withdrawal of IRB approval**

An investigator shall report to the sponsor a withdrawal of approval by the investigator's reviewing IRB as soon as a possible, but **no later than 5 working days** of the IRB notification of withdrawal of approval.

CONFIDENTIAL

### **8.3.2 Investigator reporting: notifying the IRB**

Federal regulations require timely reporting by investigators to their local IRB of unanticipated problems posing risks to subjects or others. The following describes the NYULMC IRB reporting requirements, though Investigators at participating sites are responsible for meeting the specific requirements of their IRB of record.

#### **Report promptly, but no later than 5 working days:**

Researchers are required to submit reports of the following problems promptly but no later than 5 working days from the time the investigator becomes aware of the event:

- **Unanticipated problems including adverse events that are unexpected and related**
  - Unexpected: An event is “unexpected” when its specificity and severity are not accurately reflected in the protocol-related documents, such as the IRB-approved research protocol, any applicable investigator brochure, and the current IRB-approved informed consent document and other relevant sources of information, such as product labeling and package inserts.
  - Related to the research procedures: An event is related to the research procedures if in the opinion of the principal investigator or sponsor, the event was more likely than not to be caused by the research procedures.
  - Harmful: either caused harm to subjects or others, or placed them at increased risk

#### **Other Reportable events:**

The following events also require prompt reporting to the IRB, though **no later than 5 working days**:

- **Complaint of a research subject** when the complaint indicates unexpected risks or the complaint cannot be resolved by the research team.

CONFIDENTIAL

- **Protocol deviations or violations** (includes intentional and accidental/unintentional deviations from the IRB approved protocol) for any of the following situations:
  - one or more participants were placed at increased risk of harm
  - the event has the potential to occur again
  - the deviation was necessary to protect a subject from immediate harm
- **Breach of confidentiality**
- **Incarceration of a participant** when the research was not previously approved under Subpart C and the investigator believes it is in the best interest of the subject to remain on the study.
- **New Information indicating a change to the risks or potential benefits** of the research, in terms of severity or frequency. (e.g. analysis indicates lower-than-expected response rate or a more severe or frequent side effect; Other research finds arm of study has no therapeutic value; FDA labeling change or withdrawal from market)

### **Reporting Process**

The reportable events noted above will be reported to the IRB using the form: “Reportable Event Form” or as a written report of the event (including a description of the event with information regarding its fulfillment of the above criteria, follow-up/resolution and need for revision to consent form and/or other study documentation).

Copies of each report and documentation of IRB notification and receipt will be kept in the Clinical Investigator’s study file.

### **8.3.3 Sponsor reporting: Notifying the FDA**

Shire is required to report certain study events in an expedited fashion to the FDA. The following describes the safety reporting requirements by timeline for reporting and associated type of event:

CONFIDENTIAL

- **Within 7 calendar days** (via telephone or facsimile report)

Any study event that is:

- associated with the use of the study drug
- unexpected,
- fatal or life-threatening

- **Within 15 calendar days** (via written report)

Any study event that is:

- associated with the use of the study drug,
  - unexpected, and
  - serious, but not fatal or life-threatening
- or-
- A previous adverse event that was not initially deemed reportable but is later found to fit the criteria for reporting (reporting within 15 calendar days from when event was deemed reportable).

Any finding from tests in laboratory animals that:

- Suggest a significant risk for human subjects including reports of mutagenicity, teratogenicity, or carcinogenicity.

### **Additional reporting requirements**

Sponsors are also required to identify in IND safety reports all previous reports concerning similar adverse events and to analyze the significance of the current event in light of the previous reports.

### **Reporting Process**

Adverse events may be submitted on FDA Form 3500A (MEDWATCH Form; see Attachment [5]), or in a narrative format. If supplied as in a narrative format, the minimum information to be supplied is noted above at the beginning of section 8.3. The contact information for submitting reports is noted below:

CONFIDENTIAL

[name]. CAPT USPHS Director Division of Psychiatry Products *or* [name], Chief Project Management Staff, at [name].

#### **8.3.4 Sponsor reporting: Notifying participating investigators**

It is the responsibility of Lead Principal Investigator [name] to notify Shire and [name], Principal Investigator at Mount Sinai of all and any adverse event that meets the FDA 15-day reporting requirement criteria as note above in section 8.3.4. The same materials and timeline used to report to the FDA are used for notifying participating investigators.

#### **8.4 Unblinding Procedures**

While the safety of the subject always comes first, it is still important to seriously consider if unblinding the study follow-up and referral is necessary to ensure a subject's safety. Patients will be unblinded if in the opinion of the investigator subjects adverse events or continued participation will be unsafe to the subjects. If subjects are experiencing a decline of 30% per the clinical assessments conducted they will be withdrawn. Patient will be unblinded by our investigational pharmacist to ensure safety. We will manage the patient and report these finding to our medical monitor. In the case subject is unblinded not due to an adverse event we will notify shire within 24 hours by phone or fax, followed by a written narrative of the event within 48 hours.

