## 1.6 Research Risks & Benefits

### 1.6.1 Risk of Study Drug

Study drug risks with Vyvanse (Lisdexamfetamine Dimesylate) are decreased appetite, insomnia, upper abdominal pain, irritability, nausea and vomiting, weight decreased, dry mouth, dizziness, affect lability, rash, diarrhea, anxiety, anorexia, jittery feeling, and agitation. Patients will be told to take medication once daily in the morning and report if they have any of these effects at each visit [10].

Warnings and Precautions with Vyvanse (Lisdexamfetamine Dimesylate) are sudden death, stroke, and myocardial infarction (MI) reported in adults. Sudden death reported in children and adolescents with structural cardiac abnormalities and other serious heart problems [10]. Patients will have an electrocardiograph (EKG) prior to induction on Vyvanse (Lisdexamfetamine Dimesylate). Subjects will be monitored weekly for hypertension, tachycardia and any cardiac abnormalities. People with heart abnormalities will not be treated with amphetamines. These serious but uncommon side effects were reported by people who took Vyvanse. The following cardiovascular side effects (involving the heart and/or blood vessels) have been reported with the use of amphetamines:

- Sudden death
- Cardiomyopathy (enlargement of the heart or muscle weakness)
- Myocardial infarction (heart attack)
- Increased blood pressure
- Tachycardia (rapid heart rate)
- Palpitations (forceful, sometimes irregular heartbeats)

Vyvanse (Lisdexamfetamine Dimesylate) may exacerbate symptoms of behavior disturbance and thought disorder in patients with a preexisting psychotic disorder. Vyvanse may induce a mixed/manic episode in patients with bipolar disorder. Patients will be screened for any preexisting Axis 1 diagnosis, which would exclude them from the study.

CONFIDENTIAL

The following uncommon central nervous system side effects involving the brain and/or spinal cord have been reported with the use of amphetamine: stroke, psychotic episodes, mania, euphoria, depression, dysphoria, overstimulation, aggressive behavior, hostility, seizures, tremor, dyskinesia, exacerbation of phonic tics including Tourette's syndrome or motor tics, blurry vision, dizziness, restlessness, and headache. If during the course of the study patient develops any of these side effects including changes in mood, the study doctor will discontinue patient from the study and refer the patient to regular treatment.

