#### **4.4 Early Withdrawal of Subjects**

Patients can withdraw or take back their permission to use and share his/her health information at any time. When the patient withdraws their permission, they will not be able to take back information that has already been used or shared with others.

Patients will be made aware and instructed on how to withdraw their permission by

CONFIDENTIAL

sending a written notice to the principal investigator for the study noted on page one of their consent form. If patient withdraws their permission, he/she will not be able to stay in this study. Patients will be withdrawn if, in the opinion of the study doctor, is no longer safe for the patient to participate in the study. We can get verbal permission to follow-up the patient in the event they suffer adverse events. We will document three attempts to contact the patient via phone. If unable to contact will send the patient a certified letter. Attachment [4]

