### **5.3 Method for Assigning Subjects to Treatment Groups**

Due to the study being double blind, an unblinded research assistant will conduct the block randomization of the subjects under the supervision of the NYU pharmacy. The block randomization will choose patients to start either the Vyvanse or placebo phase for four weeks. After these four weeks there will be a two week washout, then again Vyvanse or placebo phase for another four weeks. At the end of the study, the patients will be asked safety questionnaires. The patient and the research staff will not know whether the patient is on Vyvanse or placebo. In case of an emergency, the pharmacy can break the blind with permission from the principal investigator. We will know if the patient is on Vyvanse or placebo after the blind is broken.

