### **5.8 Blinding of Study Drug**

The study drug is double blinded. The research staff; including study doctor and the patient will not know if the patient is receiving Vyvanse or placebo. The study pharmacist will know which study medication either Vyvanse or Placebo the patient is taking and can break the blind in case of an emergency.

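### Section 8.4 makes code-breaking automatic on a judgement of unsafety, without the necessity condition and permission step that would keep it apart from ordinary withdrawal

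*Combined protocol and SAP*

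**What the plan says.** Four sections of the protocol bear on this.

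- **8.4 Unblinding Procedures** begins with a caution that "it is still important to seriously consider if unblinding the study follow-up and referral is necessary to ensure a subject's safety". The rule follows at once: "Patients will be unblinded if in the opinion of the investigator subjects adverse events or continued participation will be unsafe to the subjects". The section then restates the withdrawal rule for a 30% decline, says that the investigational pharmacist does the unblinding for safety, and requires a report to the medical monitor.
- **5.3 Method for Assigning Subjects** provides: "In case of an emergency, the pharmacy can break the blind with permission from the principal investigator". It adds: "We will know if the patient is on Vyvanse or placebo after the blind is broken".
- **5.8 Blinding of Study Drug** says the study pharmacist "can break the blind in case of an emergency". It names no permission step.
- **4.4 Early Withdrawal of Subjects** says: "Patients will be withdrawn if, in the opinion of the study doctor, is no longer safe for the patient to participate in the study". It does not mention the code.

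Section 8.5 repeats the 30%-decline rule with withdrawal as its only consequence.

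**The concern.** Withdrawing a patient and opening that patient's code are different acts. The first protects the patient. The second is needed only when care depends on knowing what was taken. By tying the code-break to the judgement that participation is unsafe, 8.4 merges the two.

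Two things are at stake. First, withdrawn patients are still followed for adverse events (4.4.1), and the reporting period runs to 30 days after the last dose (8.1). The investigator must assess the association with study treatment. Under 8.3, a serious event after discontinuation is reported only if the principal investigator thinks that the drug or a procedure may have caused it. After a break, these judgements are made with the treatment known.

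Second, in a two-period crossover one known treatment reveals the patient's whole sequence. Because allocation is in blocks, that can say something about block-mates whom the same staff still titrate and rate.

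**Working it through.** **Side-by-side reading.** The plan states no figure on this point to reproduce, so the check is textual.

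| Section | Trigger | Force | Authority named | Consequence |
|---|---|---|---|---|
| 5.3 | emergency | can | principal investigator's permission | code opened |
| 5.8 | emergency | can | none (pharmacist acts) | code opened |
| 8.4 | investigator's opinion that adverse events or continuing are unsafe | will be | investigator's opinion | code opened |
| 4.4 | study doctor's opinion that continuing is unsafe | will be | study doctor's opinion | withdrawal only |

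1. Section 8.4 differs from 5.3 in trigger, force and authority, and from 5.8 in trigger and force.
2. The triggers in 8.4 and 4.4 are nearly the same, so a patient withdrawn for safety under 4.4 will normally also meet 8.4.
3. Not every such exit need be an emergency. Section 1.6.1 lists nervous-system effects, ending with "blurry vision, dizziness, restlessness, and headache", and says that for any of them "the study doctor will discontinue patient from the study and refer the patient to regular treatment". It does not mention unblinding. Whether such an exit counts as unsafe under 8.4 is left to the investigator.
4. For a 30% decline the text is ambiguous. In 8.4 the sentence about the pharmacist follows that rule directly; 8.5 gives the same rule without unblinding, which suggests that these patients stay blinded.

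**Information about block-mates.** This is a conditional bound, not an estimate. It assumes 1:1 balanced blocks of size b and staff who know both block size and block membership. The documents give no block size.

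- With one sequence known, the other b − 1 members include b/2 with the opposite sequence.
- Guessing the opposite sequence for all of them gives b/2 correct, against (b − 1)/2 by chance. The gain is b/2 − (b − 1)/2 = 0.5 correct guesses, whatever b is.
- The probability of a correct guess per mate is b/(2(b − 1)): 1.00 for b = 2, 0.67 for b = 4, 0.60 for b = 6 and 0.57 for b = 8.
- Two breaks in one block tell something only if both patients have the same sequence, which has probability (b/2 − 1)/(b − 1). The gain is then 1, so the mean gain is 0.33 (b = 4), 0.40 (b = 6) or 0.43 (b = 8). On average, a second break in the same block adds nothing to the 0.5 from the first.
- Set against the 50 treated patients, 0.5/50 = 1% per break at most.

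This counts guesses. It is not a bias in any treatment estimate.

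**The case against.** The strongest reply is that the sections can be read together. Section 8.4 opens with a necessity caution and names safety as the purpose, nothing in it waives the permission in 5.3, and breaks go to the medical monitor. That softens the conflict, but the sentence that tells a site what to do carries no condition. A site that follows it as written would open codes that 5.3 does not call for.

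Several stronger readings are tempting, and the documents do not support them.

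- A reader might infer that 5.3 and 5.8 set an emergency-only rule that 8.4 breaks outright. Neither says *only*; an emergency is simply the one reason each names.
- A reader might infer that every headache or dizziness exit under 1.6.1 will be unblinded, or that breaks will be frequent. Section 1.6.1 is silent on the code, and no expected number of breaks is given.
- A reader might infer that the primary comparison is compromised. Follow-up after withdrawal covers adverse events and concomitant medication (4.4.1), so the withdrawn patient's own efficacy ratings would largely precede the break. The documents do not show that the blinded staff know block size or membership: allocation is handled by an unblinded assistant and the pharmacy, and the two sites have separate staff and pharmacies. The Barkley SCT Scale, on which power is based, comes from a self-report instrument (1.1), so staff knowledge reaches it only indirectly, for example through titration. The ADHD-RS, also named as a primary measure in Section 2, is somewhat more exposed.

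It is also fair to say that knowing about amphetamine exposure can help at referral. That is a reason to keep a needs-based break available, not to make the break automatic.

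**Conclusion.** The point holds as a minor flaw in the wording of 8.4. The unblinding rule has no necessity condition, does not mention the permission step in 5.3, and attaches a code-break to a judgement that 4.4 answers with withdrawal alone. The most direct consequence is unblinded adverse-event follow-up and relatedness assessment for patients whose care did not need the code. Leakage to block-mates is possible but slight, and depends on staff knowledge that the documents do not establish. The effect on the primary estimate is likely negligible. It cannot be quantified, because the plan gives neither the block size nor the number of breaks expected. The conclusion assumes that some safety withdrawals are not emergencies and can be managed without knowing the treatment. The plan's discontinuation rules make that plausible but do not say how often it would occur.

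**What to change.** Put one rule in 5.3, 5.8 and 8.4:

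- The code is opened, with the principal investigator's permission, only when knowing the treatment is needed to manage the patient's emergency or immediate safety.
- Withdrawal, including withdrawal for a 30% decline, does not by itself open the code.
- Where possible, the treatment is disclosed only to those treating the patient, so that staff who rate and titrate other patients stay blinded.

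This is a wording change. It alters no analysis, sample size or visit, and safety-driven unblinding stays available. The downside is that some withdrawn patients and their onward clinicians would not learn the treatment at the time of withdrawal.
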